Tuberculin PPD – This drug is used as part of a tuberculin PPD test as performed by injecting .1mL of purified tuberculin PPD subcutaneously in the skin. This is the standard dosing for a test to determine if a patient is infected with *Mycobacterium tuberculosis*.

Lidocaine/epinephrine – 3 mL injection at the biopsy site. Lidocaine-HCL 1% w/ epinephrine (1:100,000)

- b. Justification and safety information if FDA approved drugs will be administered for non-FDA approved indications or if doses or routes of administration or participant populations are changed.

N/A

- c. Justification and safety information if non-FDA approved drugs without an IND will be administered.

N/A An IND has been given approval to proceed.

7. Study Statistics

- a. Primary outcome variable.
Percent PP-NRS reduction between baseline and week 12.
- b. Secondary outcome variables.

Analysis of PN-IGA, PROMIS Itch Questionnaire, PAS, 5D Pruritus Score, DLQI, HADS, and EQ-5D and detect differences between baseline through Week 12. An ordinal regression will be used because these are non-parametric, ordinal scales.

Approval Date: 3/16/2022
Principal Investigator: [name]
Application Number: IRB00262268

c. Statistical plan including sample size justification and interim data analysis.

The trial arms of PN and CPUO will be used to conduct subsequent analyses of treatment efficacy. We will treat a p-value of <0.05 as statistically significant, and all tests will be two-tailed. For the primary endpoint, ANOVA will be used to analyze differences in percent PP-NRS reduction (baseline and week 12) with the inclusion of other covariates. We will use a Least-Square means to account for missing data or unbalanced design. We will conduct a two-way analysis of the response variable (PP-NRS percent reduction) by classification variables: specifically, whether the patient has PN or CPUO, and week of treatment. We can derive all LS-means differences from every permutation of week or diagnosis, relative to Week 0 (baseline, prior to treatment). We will incorporate a 95% confidence limit for a significant difference in LS-mean difference between the control group and other groups.

Unlike the primary efficacy endpoint, the secondary endpoints do not have explicit, clinically meaningful changes outlined in the literature. As such, we will look for significant downregulation in itch assessments, and significant improvements in quality of life and sleep measures.

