Secondary aims will be analyzed using appropriate statistical tests as outlined below, and missing data will be corrected with Multiple Imputation (MI) and we will assume that missing data is Missing at Random (MAR).

For secondary analyses, a multivariable logistic regression will be used to calculate the odds ratios of different study arms (PN and CPUO) achieving a 4-point reduction in PP-NRS and in SD NRS.

To analyze the PN-IGA, PROMIS Itch Questionnaire, PAS, 5D Pruritus Score, DLQI, HADS, and EQ-5D and detect differences between baseline through Week 12, an ordinal regression will be used because these are non-parametric, ordinal scales.

IgA for PN is not validated in the US, so we are using it as an additional secondary efficacy measure. Appendix D has a simplified version we are applying to this study. Eczema and psoriasis IgA are similarly qualitative. Analysis of PN/CPUO IgA will be an ordinal scale based on qualitative scaling determined at the site visit. We will analyze IgA with an ordinal regression, same as other scales mentioned above.

Atopy will be defined as a binary variable where patients have 2 out of 3: underlying history of atopic dermatitis, history of seasonal allergies, or asthma.

Among PN patients taking 200 mg of abrocitinib, we will use a linear regression to compare PP-NRS reduction from baseline with week 12, among PN patients with atopy and PN patients without atopy.

Approval Date: 3/16/2022
Principal Investigator: [name]
Application Number: IRB00262268

d. Early stopping rules.

Patients may withdraw at any time or they will be asked to end participation if the physician determines that discontinuation is in the patient's best interest. Data collected may be used if any endpoints are reached.

8. Risks

a. Medical risks, listing all procedures, their major and minor risks and expected frequency.

Foreseeable and known risks of study drug

There is a risk that participants might experience discomfort or side effects with the use of the study drug or procedures. Some of them are still unknown at this stage. In some cases, **side effects can be serious, long-lasting, permanent, or life-threatening**. The study doctor is trained to take the appropriate measures to reduce risks and limit any discomforts you may experience.

Side Effects:

- The most commonly reported side effects are:
 - Nausea (1 in 7 people)
 - Nasopharyngitis (1 in 8 people)
 - Headache (1 in 25 people)
- Rare but serious side effects include:

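### As most naturally read, the primary two-way analysis keeps Week 0 as a response level (always 0) and has no patient term, so its standard errors and 95% limits are generally not valid; the efficacy contrast is conservative to mildly liberal, the PN-versus-CPUO contrasts too liberal

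*Combined protocol and SAP*

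**What the plan says.** Section 7a defines the primary outcome as "Percent PP-NRS reduction between baseline and week 12", which is one number per patient.

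Section 7c then describes the analysis in several steps:

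- The method: "ANOVA will be used to analyze differences in percent PP-NRS reduction (baseline and week 12) with the inclusion of other covariates". The covariates are not named.
- The model: "We will conduct a two-way analysis of the response variable (PP-NRS percent reduction) by classification variables", with the factors given as "specifically, whether the patient has PN or CPUO, and week of treatment".
- The contrasts: "We can derive all LS-means differences from every permutation of week or diagnosis, relative to Week 0 (baseline, prior to treatment").
- The limits: 95% confidence limits for a "significant difference in LS-mean difference between the control group and other groups".
- Missing data and imbalance: "We will use a Least-Square means to account for missing data or unbalanced design".

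Tests are two-sided at 0.05. The schedule in Section 4a collects PP-NRS at Weeks 0, 2, 4, 8, 12 and 16. Neither the primary analysis nor any other part of the plan mentions a patient effect, a repeated-measures structure or a covariance matrix.

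**The concern.** Section 7a points to one value per patient. Section 7c points to several rows per patient, with week as a factor and Week 0 as the reference. If the model is fitted as described, two things go wrong together.

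1. Percent reduction at Week 0 is 0 for every patient by definition. That cell has no variance, but it still counts in the pooled error.
2. Visits from the same patient are treated as independent.

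The first makes the pooled error too small for Week 12. The second makes it too large or too small, depending on the contrast.

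This is the only analysis named for the primary endpoint. Section 4f ties a later placebo-controlled study to whether these data point to efficacy. The contrast closest to the primary objective in Section 2 is Week 12 against Week 0 within a diagnosis, so its limits should be right.

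**Working it through.** **Inputs from the plan.** Response, factors, Week 0 reference, 95% limits and two-sided 0.05 are from Section 7c; visit weeks are from Section 4a. The plan states no N, SD, correlation or power, so it has no figure of its own to reproduce.

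**Assumptions.** 5, 10 or 20 patients per diagnosis; within-patient correlation rho of 0.3, 0.5 or 0.8; post-baseline SD constant at 30, or rising from 15 at Week 2 to 32 at Week 12 (linearly or in equal steps, then held). Data are normal, with no true effect, no dropout and no covariates. The model has diagnosis-by-week cells, and k is the number of week levels including Week 0.

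**Constant SD (sigma), as worded.** One of k cells has zero variance, so MSE = sigma² × (k − 1)/k.

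- Week 12 minus Week 0 within a diagnosis. The true variance is sigma²/n and the model uses 2 × MSE/n. SE ratio (model/true) = sqrt(2(k − 1)/k): sqrt(1.6) = 1.26 for k = 5 and sqrt(1.667) = 1.29 for k = 6. The interval is too wide.
- PN minus CPUO at Week 12. SE ratio = sqrt((k − 1)/k): 0.89 for k = 5 and 0.91 for k = 6. Too narrow.
- PN minus CPUO averaged over weeks. SE ratio = 1/sqrt(1 + (k − 2) × rho). For k = 5 and rho = 0.5 this is 1/sqrt(2.5) = 0.63. Too narrow.

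**Rising SD, as worded.** With a linear rise the SDs at Weeks 2, 4, 8 and 12 are 15, 18.4, 25.2 and 32. MSE = (0 + 225 + 338.6 + 635.0 + 1024)/5 = 444.5. For Week 12 minus Week 0 the SE ratio is sqrt(2 × 444.5/1024) = 0.93. For PN minus CPUO at Week 12 it is sqrt(444.5/1024) = 0.66. Over the rising patterns and k = 5 or 6, the first ratio runs from 0.93 to 1.05.

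**Weeks 0 and 12 only (k = 2).** The Week 12 minus Week 0 ratio is 1.00. The PN minus CPUO ratio at Week 12 is 1/sqrt(2) = 0.71, so type I error is about 2 × (1 − Φ(1.96 × 0.707)) = 16.6%.

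**Patient term with one pooled within-patient error, Week 0 kept, constant SD.** (SE ratio)² = 2[(k − 1) − (k − 2) × rho]/k. This is 1 only at rho = 0.5 or k = 2. At k = 5 and rho = 0.8 it is 0.64, so the ratio is 0.80 and type I error about 11.7%.

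**Simulated type I error, nominal 5%.**

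| Analysis and contrast | Constant SD | Rising SD |
|---|---|---|
| As worded, 5 or 6 week levels: Week 12 vs Week 0 | 1.2–2.4% | 4.0–8.6% |
| As worded, 5 or 6 levels: PN vs CPUO at Week 12 | 7.3–9.6% | 14.4–20.7% |
| As worded, 5 or 6 levels: diagnosis main effect (both SD patterns) | 14.2–35.9% | 14.2–35.9% |
| Weeks 0 and 12 only: Week 12 vs Week 0 | 5.2–6.8% | – |
| Weeks 0 and 12 only: PN vs CPUO at Week 12, with interaction | 16.3–17.5% | – |
| Weeks 0 and 12 only: diagnosis main effect | 4.3–6.8% | – |
| Patient term, pooled error, Week 0 kept, 5 or 6 levels: Week 12 vs Week 0 | 2.8–13.1% | 7.0–21.5% |
| Week 0 not a data row, no patient term: Week 12 mean vs zero | 5.0–6.6% | 11.1–16.0% |
| Random intercept, Weeks 2–12: Week 12 mean vs zero | 4.8–5.3% | about 13–15% |
| One Week 12 value per patient | 4.7–5.3% | 4.7–5.3% |

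Repeat simulations under similar assumptions reached about 3%, 9% and 22% at the upper ends for, in turn, Week 12 vs Week 0 with constant SD, the same with rising SD, and PN vs CPUO at Week 12. The rounded bands in the conclusion allow for this.

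**The case against.** The strongest reply is that the wording does not settle the model. Sections 7a and 7c both mention baseline and Week 12, which could mean two time points only. A repeated-measures ANOVA may be intended. The reference to Week 0 may simply restate how percent reduction is defined, with Week 0 not a data row. This stands in part: with Weeks 0 and 12 only, the efficacy contrast is near nominal. But week is named as a classification factor and differences are promised across weeks, so the multi-week reading is the natural one. The alternatives do not give the same error rates, and neither a simple patient term nor merely dropping Week 0 is safe when SD rises.

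A second reply is that the large errors concern PN versus CPUO, which no objective asks for. That is right, and it limits the weight of the point. It is also fair that the size rests on assumed N, SD and correlation, that the unnamed covariates were not modelled, and that Week 16 (the sixth level) lies outside the stated endpoint.

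A reader might infer that the plan's efficacy p-value is too small. The figures do not support that: with constant SD it is too large, and with rising SD it ranges from slightly too large to mildly too small. A reader might also infer that the control-group phrase shows a missing comparator. It most naturally means Week 0, and only the wording needs correcting.

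**Conclusion.** The point holds, at the level of something that should be fixed. Read naturally, Section 7c puts a constant-zero level and correlated visits into one pooled error. Estimated means from complete data are not biased by this; the standard errors, limits and p-values are generally not valid, in a direction that depends on the contrast.

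Under the stated assumptions, multi-week type I error for Week 12 versus Week 0 is about 1–3% with constant SD and 4–9% with rising SD. PN versus CPUO runs at about 7–22% at Week 12 and 14–36% for the main effect. With Weeks 0 and 12 only, the efficacy contrast is at 5–7% and PN versus CPUO at Week 12, with an interaction, at 16–18%. Adding a patient term with one pooled error while keeping Week 0 in a multi-week model is not a repair (about 3–22%).

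Three nearby matters are not part of this error: how alpha is shared between the diagnoses, which covariates are meant, and how a missing Week 12 value is handled (multiple imputation is stated for the secondary aims). Clarifying them would be useful but is optional.

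**What to change.** Reword Section 7c as follows.

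- Remove Week 0 as a response level.
- Make the primary analysis the Week 12 percent reduction, one value per patient, reported as the mean in each diagnosis with a 95% CI against zero (one-sample t), using that diagnosis's own Week 12 variance.
- Reword the control-group sentence so that the limits refer to change from baseline.
- Label any PN-versus-CPUO comparison as secondary and base it on one Week 12 value per patient.
- If a longitudinal model is kept as supportive, fit it to post-baseline visits only, with an unstructured within-patient covariance (or at least week-specific variances) and small-sample degrees of freedom. A random intercept alone is not enough when SD rises.

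The cost is a text change to one section, with no new patients, visits or data.

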 - HIV screening test. You may be asked to sign a separate State of Maryland consent form for this HIV test. If the HIV test is positive it does not always mean you are infected with the HIV virus. It does mean you will need further testing and you will receive counseling about this. The law requires us to report positive tests to the health department. This reporting will include information that identifies you (for example name, date of birth, home address, phone number, etc.) as required by Maryland law. The health department may use this information to contact you for further follow up and/or to help conduct health surveillance activities aimed at preventing or controlling diseases.
 - Only for participants with known history of HIV: CD4+ T cell count and viral load will be evaluated at screening and

at the end of the study drug period. This will be approximately 10 mL (less than one tablespoon) blood in addition to total amount of blood.

- Pregnancy testing: only for women capable of having children: by blood test at the first study visit and urine sampling test every 4 weeks at site visit.
- **For Study Visits 2 through 7 (Week 0 – 16) the following procedures will be done according to the schedule above: Visits will be conducted within the specified week or within +/- 5 days of the intended week.**
 - Dispensing of Investigational Drug: All participants will receive abrocitinib beginning at visit 2. This will be taken as a daily oral dose of 200mg in tablet form. This therapy will continue for 12 weeks (through visit 6).
 - Electronic diary: Participants will be asked to complete a diary daily in the morning. This will include questionnaires to evaluate the severity of symptoms such as itch and pain and asking participants to rate their quality of sleep during the last night. The completion of the diary will take approximately 10 minutes. The study doctor or site staff will train participants on how to use the diary during Visit 1 and give you instructions on how to complete these assessments. This diary must be returned to the site at the end of study visit.

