Itch Diary Review/compliance			X	X	X	X	X
Skin biopsy		X				X	
Plasma/PBMC isolation from blood draw		X				X	X
Labs from Blood Draw (CMP, CBC, Lipid panel, IgE)	X	X	X	X	X	X	
Patient who are HBcAB-positive and HBV DNA-negative at baseline require HBV DNA monitoring		X	X			X	

Approval Date: 3/16/2022
Principal Investigator: [name]
Application Number: IRB00262268

b. If your study involves data/biospecimens from participants enrolled under other research studies with a written consent or under a waiver of consent, please list the IRB application numbers for those studies. Please note: Certificate of Confidentiality (CoC) protections applied to the data in source studies funded by NIH or CDC will extend to this new study if the funding was active in 2016. If this situation applies, Section 36, question 6 in the application will need to be answered "Yes" and "Hopkins Faculty" should be selected in question 7. No other documents are required.

N/A

c. Study duration and number of study visits required of research participants.

Participants will be in this trial for up to 20 weeks including screening and follow-up.

d. Blinding, including justification for blinding or not blinding the trial, if applicable.

This study will not be blinded. All participants will receive study drug therefore blinding is not applicable.

e. Justification of why participants will not receive routine care or will have current therapy stopped.

Participants will need to stop current therapy in order to qualify for the study. In order to clearly elucidate the efficacy of abrocitinib against PN and CPUO, it is important for concurrent therapies to be halted. It is also important to note that the majority of therapies offered to these patients have poor efficacy in controlling PN and CPUO.

Participants will continue to receive other routine care.

f. Justification for inclusion of a placebo or non-treatment group.

There is no placebo group in this study. As this is an early phase, small study, we will not include a placebo group. If the data is suggestive of efficacy, a full blinded, and placebo-controlled study will be done.

g. Definition of treatment failure or participant removal criteria.

Approval Date: 3/16/2022
Principal Investigator: [name]
Application Number: IRB00262268

Discontinuation Criteria

Discontinuation from Study Treatment

Temporary Interruption of Investigational Product

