PBMCs will be isolated from patient whole blood at the same time points above, at Week 0, at Week 12, and at Week 16. To analyze multiple immune cell populations, we will use the Maxpar Direct Immune Profiling Assay from Fluidigm, which uses Cytometry by time-of-flight (CyTOF), a novel variant of conventional flow cytometry. This kit supplies 30 metal-tagged antibodies as a dry pellet, with additional channels/metal tags allowing for additional targets. 37 immune cell populations can be characterized from PBMCs, and CyTOF technology will allow for complete protein quantification of all selected markers.

These tests will not be performed at a CLIA certified laboratory because these are not clinical grade tests and are designed only for research purposes. No results from these tests will be shared with participants as these are not intended for diagnostic purposes.

5. Inclusion/Exclusion Criteria

Inclusion Criteria:

- Males or female participants between ages 18-80 years at time of signing informed consent
- A clinical diagnosis of prurigo nodularis, defined by the presence of at least 10 pruritic nodules on at least 2 different anatomic locations (with each arm, leg, and anterior and posterior trunk considered distinct anatomic locations)
OR
- Subject has ongoing chronic pruritus of unknown origin, which must be present on multiple segments on the body. CPUO patients must not have known dermatologic or systemic conditions, that in the opinion of the investigator, are the cause of patient's pruritus
- Subject has moderate to severe pruritus, defined as average worst itch numeric rating scale – PP-NRS ≥ 7 (range 0-10, higher score indicating greater degree of pruritus severity) in the 7 days prior to the Screening Visit.
- Must read and understand the informed consent approved by the institutional review board (IRB) governing the site and provide written informed consent.

Sex

Approval Date: 3/16/2022
Principal Investigator: [name]
Application Number: IRB00262268

a) Female participants are eligible for the study if they are not pregnant, planning to become pregnant or breastfeeding during the study and one of the following applies:

- Female participant is not a WOCBP: Female patients of non-child-bearing potential are not required to use birth control and they are defined as:
 - Women who are infertile due to surgical sterilization (hysterectomy, bilateral oophorectomy, or tubal ligation)
 - Post-menopausal – defined either as

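### The 4-point SD-NRS responder model, the plan's only SD-NRS analysis, includes patients who may start too low to respond, so its PN-versus-CPUO odds ratio could partly reflect room to improve

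*Combined protocol and SAP*

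**What the plan says.** Section 7c (Statistical plan) names the method: "For secondary analyses, a multivariable logistic regression will be used". The task it gives this model is: "calculate the odds ratios of different study arms (PN and CPUO) achieving a 4-point reduction in PP-NRS and in SD NRS". The section lists no covariate for this model, sets no baseline limit on who enters it, and gives no time point for the 4-point fall. The only other mention of covariates is for the primary ANOVA ("with the inclusion of other covariates"), and those are not named either.

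Section 5 sets an entry floor for itch: "PP-NRS ≥ 7 (range 0-10, higher score indicating greater degree of pruritus severity", averaged over the week before screening. Neither the inclusion nor the exclusion criteria mention SD-NRS. The schedule in Section 4a first collects SD-NRS at Visit 2 (Week 0).

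SD-NRS is missing from the secondary outcomes in Section 7b and from the scales assigned to ordinal regression in Section 7c. The responder model is therefore its only specified analysis. Yet Section 7c says of the secondary endpoints that "we will look for significant downregulation in itch assessments, and significant improvements in quality of life and sleep measures".

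PN and CPUO are called arms but are diagnoses. Section 4d says: "All participants will receive study drug therefore blinding is not applicable".

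**The concern.** A fixed 4-point threshold needs a starting score of at least 4. The itch criterion makes a Week 0 PP-NRS below 4 unlikely. Nothing does the same for sleep, and a patient can have severe itch with a low sleep-disturbance score. Such a patient enters the SD-NRS denominator and cannot enter its numerator.

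The model compares two groups whose baselines the design does not balance. If one group has more low starters, or lower sleep scores in general, its odds of a 4-point fall are lower even when the drug acts equally well in both. A reader could then take a PN-versus-CPUO odds ratio as a difference in response when part of it is a difference in room to improve. No continuous SD-NRS analysis is planned that would help tell the two apart.

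**Working it through.** The plan gives no SD-NRS baseline, responder rate or group size, so there is no figure to reproduce. **Every input below is an assumption**, including the 0-10 range, which Section 5 gives only for PP-NRS.

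**1. No true difference.** Let f be the share of a group starting below 4 and p the response rate among the rest, equal in both groups. Then

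- observed response rate r = (1 − f) × p
- odds ratio = [r1/(1 − r1)] / [r2/(1 − r2)]

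With p = 0.5:

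| f, group 1 vs group 2 | r1 vs r2 | Odds ratio |
|---|---|---|
| 20% vs 20% | 0.400 vs 0.400 | 1.00 |
| 10% vs 15% | 0.450 vs 0.425 | 1.11 |
| 10% vs 20% | 0.450 vs 0.400 | 1.23 |
| 10% vs 30% | 0.450 vs 0.350 | 1.52 |

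For example, (0.45/0.55)/(0.40/0.60) = 1.23. At 10% vs 20%, p = 0.3 gives 1.17 and p = 0.7 gives 1.34.

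**2. A real difference with equal shares below 4.** Take 70% vs 50% response among those able: (0.70/0.30)/(0.50/0.50) = 2.33. With 10%, 20% or 30% of both groups below 4, the all-patient odds ratio is 2.08, 1.91 or 1.78. For 20%: (0.56/0.44)/(0.40/0.60) = 1.91.

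**3. Which remedy removes the shift?** Two mechanisms, both with no true difference between diagnoses:

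- *Flat response:* 50% respond at every baseline of 4 or more. Baselines are uniform on 0-3 (share f) and on 4-10 (share 1 − f).
- *Proportional improvement:* baselines are rounded normal with means 6.5 vs 5.5 and SD 2.2, and out-of-range values are set to 0 or 10. Each patient improves by a Beta(2, 1.3) fraction of baseline. This puts 8.6% vs 18.2% below 4.

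| Scenario | All patients, no covariate | Baseline covariate only | Restricted to ≥ 4 only | Both |
|---|---|---|---|---|
| Flat, 10% vs 20% | 1.23 | 1.12 | 1.00 | 1.00 |
| Flat, 10% vs 30% | 1.52 | 1.24 | 1.00 | 1.00 |
| Proportional | 1.62 | 1.00 | 1.40 | 1.00 |

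Neither step works alone under both mechanisms; the two together do.

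**4. Size against noise.** At an assumed 20 per group, 9/20 vs 8/20 gives an odds ratio of 1.23 with a Wald 95% CI of 0.35 to 4.31. The chance of a false p < 0.05 (two-sided Pearson test, exact enumeration, p = 0.5) is:

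| Shares below 4 | 20 per group | 10 per group |
|---|---|---|
| 20% vs 20% | 4.8% | 4.0% |
| 10% vs 20% | 5.7% | 4.6% |
| 10% vs 30% | 9.5% | 6.1% |

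**5. Price of restriction plus covariate.** Restriction alone turns the example into 9/18 vs 8/16: odds ratio 1.00, 95% CI 0.26 to 3.85. In simulations at 20 per group, using both steps raises the SD of the log odds ratio from about 0.7 to about 0.8 (flat, 10% vs 20%) or 0.92-0.95 (proportional). Root-mean-square error also rises, from about 0.7 to 0.8 and from about 0.85 to 0.92-0.95. It fell only under a large imbalance, from 1.25 to 0.98.

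**The case against.** **The model may already adjust for baseline.** A multivariable model with diagnosis as the exposure must contain something else, and Week 0 SD-NRS is an obvious candidate. This stands. A reader might infer that the plan leaves baseline out, but it only leaves the covariates unnamed. Even so, under the flat mechanism a linear baseline term alone does not remove the shift.

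**No imbalance is shown.** This also stands. A reader might infer that the PN-versus-CPUO odds ratio is biased. The documents support only that it could be, if the groups differ at Week 0 and baseline is not in the model.

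**The pull toward 1 with equal shares is not bias.** Correct. The 1.91 in step 2 answers how often all patients achieve a 4-point fall, which is a legitimate question. It differs from the question about patients able to respond, so both results deserve to be shown.

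**The remedy costs more than it gains.** In the modest scenarios the full remedy gives a larger root-mean-square error than the unadjusted all-patient odds ratio. That is the strongest argument against replacing the all-patient result. It does not argue against showing both, or against a change analysis that drops nobody.

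**PP-NRS has the same fault.** A reader might extend the point to the itch responder model. The entry floor makes a Week 0 score below 4 unlikely, although that floor applies before screening and not at Week 0. What remains is that a higher baseline leaves more room to fall. With Week 0 scores assumed to lie between 7 and 10 and proportional improvement, means of 8.5 vs 8.2 or 7.9 give odds ratios of 1.10 or 1.21. That is minor.

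**Conclusion.** The concern holds in a conditional form. The only specified SD-NRS analysis includes patients who, on an assumed 0-10 scale, may be unable to meet its definition of response. Its PN-versus-CPUO odds ratio could therefore mix response with room to improve, if Week 0 SD-NRS differs between the diagnoses and is not among the unnamed covariates.

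Under the assumptions in step 1, a null odds ratio moves to between 1.11 and 1.52 at 50% response. With equal baselines it stays at 1.00. In a small study this is well inside sampling error, and the added false significance is under one percentage point at 10% vs 20% (5.7% against 4.8% at 20 per group). The gain is mainly in interpretation. The change is worth considering but is not essential, and confidence is medium because the documents give no SD-NRS baseline, scale range or group size.

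**What to change.** In Section 7c:

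1. Add an analysis of SD-NRS change from Week 0 to Week 12 in all patients, adjusted for Week 0 SD-NRS.
2. Report the 4-point SD-NRS responder model in patients with Week 0 SD-NRS of at least 4, with Week 0 SD-NRS as a covariate, and give the number excluded in each diagnosis.
3. Show the all-patient responder result alongside.
4. State in advance which of these results leads, and give the SD-NRS range.

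Naming Week 0 PP-NRS as a covariate in the PP-NRS responder model is optional; no baseline restriction is needed there.

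This takes a few sentences and no new data, because the schedule already collects both scales at Week 0. The statistical cost is a smaller denominator and wider intervals for the restricted model, as in step 5 of the working. The PN-versus-CPUO comparison remains observational after adjustment.
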